12.1.2 Subject Consent Form

Initial verbal consenting will only be used when potential participants are not in the clinic. In these situations, the Research Nurses and CRAs will use the approved information sheet for verbal consent process. An informed consent will then be obtained either in writing in person, by mail, or electronic mail, or electronically via other electronic applications (i.e. DocuSign). Otherwise, all participants will complete written or electronic informed consent (i.e. DocuSign) informed consent prior to study participation. The study will use one written or electronic informed consent (with signature line) and one information sheet (without signature line) for patients. Documentation of initial verbal consent for study participation will be charted through progress notes and maintained in the patients' electronic medical records as required by the Institutional Review Board.

At the time of registration, the original signed and dated Informed Consent form, HIPAA research authorization form, and the California Experimental Subject's Bill of Rights (for the medical record) and three copies (for the subject, the research record, and the Coordinating Center) must be available. All Institutional, NCI, Federal, and State of California requirements will be fulfilled.

12.1.3 Data Collection Forms and Submission Schedule

All data will be collected from wearable devices (accelerometer) and electronic PROs. Data will be sent to the location identified in Section 12.1.1 and stored in a secure location.

Preoperative Functional Assessments – For prehabilitation needs (referrals to PT/OT), we will use the following: **6-Minute Walking Test (6MWT)** – This is a performance-based, 15 minute measure of functional exercise capacity.⁷⁷⁻⁷⁹ It measures the distance that an individual is able to walk over a total of six minutes on a hard, flat surface. Patients are allowed to self-pace and rest as needed. **Timed Up & Go (TUG)** - This is a test of physical mobility. The test, measured in

seconds, is the time it takes for an individual to stand up from a standard arm-chair (approximate seat height of 46 cm), walk a distance of 3 meters (10 feet), turn, walk back to the chair, and sit down again.⁸⁰ **Short Physical Performance Battery (SPPB)** - This is a tool designed to quantify physical performance and decline over time. The test focuses primarily on lower extremity function and includes a 4 meter walk to measure gait speed, one chair stand (followed by 5 timed chair stands, if the first is successfully completed), and balance stands with the feet held in different positions for 10 seconds each. The test takes about 10 minutes to complete.^{81, 82}

Health literacy screen – A brief 1-item screening will be performed following informed consent to screen for limited health literacy.

Sociodemographic and health status – This tool covers social and demographic factors, including patient's age, sex, race/ethnicity, education, marital status, living situation, employment, income, religious preference, tobacco history, and symptoms. Patients will complete the tool at baseline.

General Well-Being – this will be assessed using one question: Compared to yesterday, how do you feel (worse, same, better).

MD Anderson Symptom Inventory (MDASI) - The MDASI is a validated measure of 13 common cancer-related symptoms: pain, fatigue, nausea, sleep, distress/anxiety, shortness of breath, memory, appetite, dry mouth, drowsiness, sadness, vomiting, and numbness/tingling. Each symptom's severity is rated on a 10-point scale. A score of 1-3 indicates mild intensity, and 4-10 moderate to severe intensity. Patients also rate how much their symptoms interfered with 6 common functional domains: walking, activity, working/housework, social relationships, enjoyment of life, and mood. A movement of 1.2 points is clinically meaningful. The MDASI has been validated in surgical populations; Cronbach Alpha reliability ranges from 0.82 to 0.94.^{46, 83}

Functional Activity (Actigraph) – Based on published recommendations on best practice in use of accelerometry⁸⁴⁻⁸⁷, we will initiate several parameters to ensure that the data captured is reliable. First, data will be collected in 1 second epochs and reintegrated to 60 second epochs for analysis. Non-wear time will be defined as 60 minutes of continuous 0 counts. A minimum of 4 weekdays and 1 weekend day with at least 600 minutes (10 hours) of daily wear time will be considered valid. In order to be considered a valid day, patients need to wear the accelerometer for at least 10 waking hours (600 minutes). Data capture will focus on the following: 1) number of steps taken per day and 2) sedentary time. Recommended activity counts per minute (cpm) cutpoints will be used to categorize sedentary time (<100 cpm) from light-intensity physical activity (100–1951 cpm) and moderate/vigorous intensity physical activity (≥ 1952 cpm).

Comprehensive Complications Index (CCI) - The CCI[®] summarizes the entire patient postoperative experience with respect to complications (on a scale from 0 to 100), and is based on the established Clavien-Dindo classification. The CCI[®] was validated in a study with 1299 participants, and external validity was tested in a randomized trial evaluating pancreas, esophageal, and colon resections.^{88, 89}

Readmissions - Electronic health record audits will capture: 1) 30, 60, and 90 day inpatient readmissions, 2) reasons for readmissions, and 3) ER visits. If the patient seeks emergent care outside of the primary institution, the patient's permission will be obtained to review these records.

Focus Group Guides - The semi-structured questions for focus groups are designed to solicit patient/families and surgeon/nurse perspectives on the following: 1) overall perceptions of perioperative care; 2) unmet needs during pre-and postoperative care; 3) greatest challenges before and after surgery; 4) postoperative recovery process at home; 4) use of telemonitoring application for communication (surgeon/nurses); 5) use of telemonitoring dashboard to guide clinical care (surgeon/nurses).

Exit Surveys – This survey contains several open-ended questions that participants in the perioperative telemonitoring arm will complete. The participants will provide information via written comments. The questions are designed to solicit feedback on the following: 1) on-boarding and setup process; 2) use and setup process of accelerometer; 3) value of monitoring PROs and functional activity;; 4) satisfaction with the timing of the telemonitoring (starts before surgery and continues up to 3 months after discharge from hospital); 5) satisfaction with the methods/technology used (mobile application, wristband watch) 6) most useful components of the telemonitoring for helping with postoperative recovery; 7) likes/dislikes of the program; 8) challenges and limitations of telemonitoring; and 9) suggestions on areas for improvement.

12.1.3.1 Eligibility Checklist

No eligibility checklist will be used in this study as the eligibility criteria is short.

12.1.3.2 Prior Therapy Forms and On-Study Forms

No prior therapy forms and on-study forms will be used in this study.

12.2 Protocol Deviations

12.2.1 Deviation Policy

This protocol will be conducted in accordance with COH’s “Clinical Research Protocol Deviation Policy” located at

<http://www.coh.org/dsmc/Documents/Institutional%20Deviation%20Policy.pdf>.

Deviations from the written protocol that could increase patient risk or alter protocol integrity require prior IRB approval of a single subject exception (SSE) request. In addition, if contractually obligated, the sponsor must also approve the deviation. IRB pre-approved SSE protocol modifications are considered an amendment to the protocol and not a deviation. The submission of a deviation report is not required.

Brief interruptions and delays may occasionally be required due to travel delays, airport closure, inclement weather, family responsibilities, security alerts, government holidays, etc. This can also extend to complications of disease or unrelated medical illnesses not related to disease progression. The PI has the discretion to deviate from the protocol when necessary so long as such deviation does not threaten patient safety or protocol scientific integrity. Examples include, but are not limited to: a) dose adjustments based on excessive patient weight; b) alteration in treatment schedule due to non-availability of the research participant for treatment; c) laboratory test results which are slightly outside the protocol requirements but at levels that do not affect participant safety. These instances are considered to be deviations from the protocol. A deviation report will be submitted to the DSMC/IRB within five days.

12.2.2 Reporting of Deviations

All deviations will be reported to the COH DSMC within five days. The DSMC will forward to report to the IRB following review.

12.2.3 Resolving Disputes

The COH Investigational Drug Service (IDS) cannot release a research agent that would cause a protocol deviation without approval by the PI. Whenever the protocol is ambiguous on a key point, the IDS should rely on the PI to clarify the issue.

In situations where there is misperception or dispute regarding a protocol deviation among the persons involved in implementing the protocol, it is the responsibility of the PI to resolve the dispute and the PI may consult with the DSMC chair (or designee) to arrive at resolution.

13.0 Statistical Considerations

13.1 Study Design

This is a prospective, randomized, mixed methods, comparative effectiveness trial (1:1 randomization) of perioperative telemonitoring in cancer surgery (GI, GU, GYN). These cancer sites were selected because the surgical procedures, extent of resection, and expected surgical outcomes are similar. Our CER question is: What are the comparative effectiveness of remote perioperative telemonitoring care as compared to the surgeon (and surgical team) only perioperative care? This research focuses on comparing the two groups to identify which approach will most benefit cancer surgery patients.

In Aim 1, clinically significant changes in functional recovery (accelerometer daily step count) and related secondary patient-centered outcomes (sleep, sedentary time, symptoms, symptom interference with activity) will be tested over time by the comparators (remote perioperative telemonitoring care versus surgeon only perioperative care). The **primary outcome** is the clinically significant change in accelerometer daily step count over time. In Aim 2, we will test changes in postoperative complications and related secondary surgical outcomes (hospital readmissions) by the comparators. Here, the **primary outcome** is postoperative complications in the 30 days after surgery. In Aim 3, we will compare early withdrawal (dropout, loss of device) between the comparators. Finally, in Aim 4, we will qualitatively explore the perioperative telemonitoring experience from the patients, families, and surgeon's/nurse's perspective. This aim was included to explore perioperative care-related experiences (acceptability, technology usability, uptake/integration) among patients, families, and surgeons/nurses through qualitative focus groups and open-ended exit surveys. The data will be used to refine and assure model fidelity in future studies. It will also guide future integration into other healthcare system settings.

13.2 Statistical Analysis Plan

Data Management - We expect a total of 12 symptom evaluations per participant over the 3-4 month study duration. With a total sample of 332, this yields approximately 4,000 data collection encounters overall. We expect a large number of daily steps data observations per subject, as functional recovery data will be continuously recorded on a daily basis over the study duration.

Data will be transferred in real-time (within 2 minutes of participant completion) from TapCloud™ to a REDCap (Research Electronic Data Capture) study database. Daily step count will be continuously transferred to the study database in real-time. The database resides in secure COH research networks for research team access only. An assigned master's-level Statistical Research Associate (SRA) with paid effort on the project will be responsible for coordinating monthly data transfer, auditing, and data cleaning. In the process of data transfer and mergers, the study biostatistician ([name]), SRA, and TapCloud™ representative will audit and clean the data, apply formats in statistical software, and export data into REDCap database.

Handling Missing Data and Lost to Follow-Up - We will integrate the following strategies to prevent, detect, and remedy missing data in real time. First, participants will receive a total remuneration of \$50 for providing data. Second, research staff will provide telephone/email reminders before each of the scheduled data collection timepoints to maximize adherence. Regular contact will also be provided to remind participants to wear the accelerometer. Third, research staff will provide each participant with a simple study calendar with data collection dates. Fourth, if no data is completed by participants, research staff will contact the participant in real-time to engage and assess. The Statistical Methods section below describes how data missing not at random will be handled in the analyses.

Preliminary Analysis - Descriptive statistics will be used to summarize all variables. Characteristics of participants at baseline will be reported in tabular form using appropriate descriptive statistics. Prior to hypothesis testing, the relationship between demographic variables and primary outcome variables (daily step count, postop complications) will be examined. Significant relationships/correlations will guide the addition of demographic variables to the analysis.

Heterogeneity of Treatment Effect - Exploratory use of interaction terms will assess whether significant effects of the study intervention differ by sex or by age (i.e., above vs below 70 years). If found to be present, any such heterogeneity of treatment effect, not having been hypothesized in advance, will be reported as a preliminary finding that awaits confirmation in future studies.

Internal/External Validity and Avoidance of Bias - To limit possible confounding of the primary results, analyses of the prespecified hypotheses will be adjusted for covariates (age, sex, physical fitness at pre-surgical baseline). To assess the representativeness of study participants, their demographic characteristics (sex, age) will be compared to those of eligible patients who are approached for consent but decline to participate in the study. Our digital engagement platform will initiate reminder systems to reduce loss to follow-up.

Statistical Methods by Study Aims - Characteristics considered as potential covariates in all analyses will be age, sex, surgical technique, residential setting, and physical fitness at preoperative baseline. Any covariate that improves the model's fit to the observed data will be retained in the final analysis.

The analyses for Aims 1-3 will be by intention to treat (ITT); the ITT population will include all subjects who have given informed consent, been randomized to intervention or control arm, and undergone the planned cancer surgery.

Aim 1 – Allowing for an anticipated 20% attrition in use of accelerometer by Day 14 across both trial arms, an initial sample size of 332 (randomized 1:1) will provide (per East 6.5 software)

80% power to detect the hypothesized 14% difference in slope due to study intervention, using a 1-sided, repeated measures-difference of slope test with alpha=0.025.

The Aim's primary endpoint will be the percent change from preoperative baseline in daily step count during the first 2 weeks post-discharge from hospital (measured on Discharge Day, Day +7, and Day +14). percent change from preoperative baseline in daily step count during the first 2 weeks post-discharge from hospital (measured on Discharge Day, Day +7, and Day +14). To recognize that these data may be missing not at random (ie, due to adverse event, distress, or withdrawal of consent), the effect of study intervention on primary endpoint will be modeled jointly with early withdrawal from data collection of that endpoint. Within the joint model, the sub-model for the primary endpoint will use generalized linear mixed modeling (with treatment and covariates as fixed factors, patient ID as random factor), while the other sub-model will analyze time to early withdrawal (Aim 3's primary endpoint) using proportional hazards regression. Similar joint modeling will be carried out for Aim 1's secondary endpoints (change from baseline in sedentary time, general symptoms, disease-specific symptoms).

Aim 2 – Because the CCI is derived from data routinely entered in the medical chart, no loss to follow-up is anticipated for this endpoint. A sample size of 332 subjects randomized 1:1 will provide (per East 6.5 software) 88% power to detect the hypothesized CCI benefit, using a 1-sided test of proportions, unpooled estimate of variance, critical p-value for efficacy=0.024, cumulative alpha=0.025.

The Aim's primary endpoint will be maximum Comprehensive Complications Index (CCI) during the 30 days post-discharge. Maximum CCI will be categorized as above vs below 15, and logistic regression will be used to evaluate the effect of study intervention. The Aim's secondary endpoint, time to hospital readmission through 90 days, will be subjected to survival analysis, handling any early withdrawal from study as a competing endpoint.

Aim 3 - The trial's sample size of n=332 will provide (per SAS software, PROC POWER for two-sample comparison of proportions) at least 80% power.

Treatment will be evaluated for association with this Aim's primary endpoint, time to early withdrawal, using proportional hazards regression. This analysis will be generated as a sub-model of the joint modeling for Aim 1.

Aim 4 - Qualitative data from exit interviews and focus groups will be analyzed using the conventional content analysis approach.⁷³ Written survey comments will be transferred to, and data from the audio-recorded focus groups will be transcribed and analyzed using HyperRESEARCH™ qualitative software. Transcripts will be imported allowing for the development of analytic categories, data coding, and review of coded data. All data will be read repeatedly to achieve immersion and obtain a sense of the whole. Then, data will be read to derive codes, and sorted into themes based on links and relationship. [name] and [name] will conduct a final validation review of the codes/themes to ensure consistency and clarity across all qualitative data. Data discordantly coded will be discussed for refinement and consensus purposes with the SAC.

The team will use a mixed methods approach to enhance interpretation of study findings. For interpretation of study findings, the exit survey and focus group data will be used to augment quantitative data in Aims 1-3 (perioperative experience with functional recovery, symptoms,

sedentary time, postoperative complications, hospital readmissions, burden of telemonitoring). One approach to qualitative analysis is to use the quantitative outcomes of interest as themes for coding the qualitative data. Therefore, each quantitative outcome of interest will have corresponding qualitative data in the participants and stakeholder's own words. The table below illustrates the connection between quantitative and qualitative data.

Quantitative Outcomes	Connections with Qualitative Data
Functional recovery/sedentary time	Patient/family partner focus groups – overall experience with postop functional recovery/sedentary time
Sleep, symptom severity, symptom interference with daily activities	Patient/family partner focus groups – overall experience with postop symptoms
Postoperative complications (Comprehensive Complications Index – CCI) and related secondary surgical outcomes (hospital readmission).	Surgeon-nurses focus groups Patient/family partner focus groups – overall experience
Early withdrawal (dropout or loss of accelerometer device)	Telemonitoring arm open-ended exit survey

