Monitoring Postoperative Recovery from Cancer Surgery is Challenging after Discharge. Due to changes in healthcare and advances in surgical techniques, surgeons are asked to discharge patients earlier after surgery. Operations that were previously associated with 10-20 day hospital stays are now outpatient or short-stay procedures. Postoperative complications that traditionally arise in the hospital are also developing in the community and at home. The current delivery model for post-discharge care is largely inefficient and not proactive.³² Home health nurses are often dispatched for unresolved acute problems. Patients may contact the hospital when acute problems arise, but are often unaware of when to contact their surgeons (RQ-3). This often requires hours or days to resolve, and is burdensome for patients, families, and the healthcare system. Delays in communicating critical conditions may escalate problems beyond outpatient care. In critical situations, emergency room visits within the same healthcare system or at a different institution occur, resulting in inefficient and fragmented care.

The burden of postoperative hospital readmissions after major cancer surgery is high.³³⁻³⁵ Depending on the tumor site, 90-day readmission rates for major cancer surgery range from 23-43%.³⁶ Published data suggest that 30- and 90-day readmission rates are 30% and 43% for cystectomy, and 22% and 35% for esophagectomy and pancreatectomy.^{36, 37} Hospital readmissions are burdensome, and result in higher 1-year mortality rates, and delays in timing and eligibility for adjuvant therapies.³³ Predictors of readmissions are similar across different tumor sites, and include functional impairments, comorbid conditions, and postoperative complications.^{36, 38}

There are Critical Knowledge Gaps on the Impact of Patient-Centered Outcomes in Cancer Surgery. The impact of routine symptom monitoring is predominantly tested in chemotherapy settings.^{39,40} These findings suggest a positive effect on patient-provider communication⁴¹⁻⁴⁴, detection of unrecognized problems^{40, 44-47}, guiding clinical care^{46, 48-50}, health outcomes⁵⁰⁻⁵⁴, and survival.⁹ Few studies are conducted in surgical oncology, and few

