4.4 Randomization and/or Dose Level Assignment

Each patient will be randomly assigned to either the remote perioperative telemonitoring or surgeon only perioperative care arm, using a stratified and blocked randomization. Strata will be defined by diagnosis (GI, GU, GYN) and surgical technique (minimally-invasive versus open). Variable block sizes will be used to maintain approximate balance and pre-assignment masking.

[figure not shown]

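### Treatment-effect heterogeneity is explored by sex but not by diagnosis, a randomisation stratum absent from every planned model, so a difference between cancer types could appear partly as a sex difference

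*Combined protocol and SAP*

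**What the plan says.** In the combined protocol and SAP, Section 13.2 (Heterogeneity of Treatment Effect) names two effect modifiers. Interaction terms will assess "whether significant effects of the study intervention differ by sex or by age (i.e., above vs below 70 years". Anything found, "not having been hypothesized in advance, will be reported as a preliminary finding that awaits confirmation in future studies".

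Diagnosis is built into the design. Section 4.4 states: "Strata will be defined by diagnosis (GI, GU, GYN) and surgical technique (minimally-invasive versus open". The synopsis lists diagnosis among the data collected.

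Diagnosis is missing from the models. One paragraph of Section 13.2 says "analyses of the prespecified hypotheses will be adjusted for covariates (age, sex, physical fitness at pre-surgical baseline". Another says "Characteristics considered as potential covariates in all analyses will be age, sex, surgical technique, residential setting, and physical fitness at preoperative baseline". The second list includes surgical technique, the other stratification factor, but not diagnosis. The Preliminary Analysis step may add further covariates, but only demographic ones.

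The reason given in Section 13.1 for pooling the three groups is: "These cancer sites were selected because the surgical procedures, extent of resection, and expected surgical outcomes are similar".

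**The concern.** Sex and diagnosis overlap in this population. GYN patients are all women; the documents do not say so, but it follows from the disease category. GU patients probably lean male, which is an assumption. A treatment-by-sex term fitted without treatment-by-diagnosis therefore contrasts two groups with different cancer mixes. If the intervention works differently in GYN or GU surgery, part of that difference goes into the sex term.

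Two things are at stake. An apparent sex finding might send later research after the wrong modifier. And the expectation of similarity that supports pooling is never checked against the treatment effect in each cancer type.

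**Working it through.** The plan gives no power, sample size or expected size for any interaction, so there is no figure to reproduce. The question is how much of a difference between diagnoses would reach the sex term if sex itself had no effect within any diagnosis.

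**Inputs from the documents.** The modifiers are sex and age (Section 13.2). Diagnosis is a stratum (Section 4.4). Enrolment is open to both sexes (Section 3.3). Aim 1 has 80% power at 1-sided alpha 0.025 (Section 13.2), used only to set a scale.

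**Assumed inputs.** The documents give no split by diagnosis or sex. I took four mixes of GI/GU/GYN and three sex splits, with women as 45%, 50% or 40% of GI paired with 25%, 10% or 20% of GU. GYN is 100% women.

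**Leakage formula.** Let w be a diagnosis's share of patients, f its proportion of women, and F = sum of w x f. If the effect differs only in that diagnosis, the fraction passing into the sex interaction (women minus men) is w x f / F - w x (1 - f) / (1 - F). For GYN the second term is zero, so the leak equals the GYN share of women.

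**Worked case** (34/33/33; GI 45% and GU 25% women):
- F = 0.34 x 0.45 + 0.33 x 0.25 + 0.33 = 0.5655.
- GYN: 0.33 / 0.5655 = 0.58.
- GU: 0.0825 / 0.5655 - 0.2475 / 0.4345 = 0.15 - 0.57 = -0.42.
- GI: 0.153 / 0.5655 - 0.187 / 0.4345 = 0.27 - 0.43 = -0.16.

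**Standard error after the fix.** The variance of the unadjusted sex interaction is proportional to 1 / [F(1 - F)]. With treatment-by-diagnosis in the model, the information on sex is the sum of w x f x (1 - f) over GI and GU only. In the worked case, F(1 - F) = 0.2457 and the GI plus GU information is 0.0842 + 0.0563 x 1.1 = 0.1460, where the factor 1.1 takes GU from 30% to 33% of patients. The ratio is sqrt(0.2457 / 0.1460) = 1.30.

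**Results over all mixes** (leaks in absolute value; ranges are over the three sex splits):

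| GI/GU/GYN (%) | GYN-only leak | GU-only leak | GI-only leak | SE ratio after fix |
|---|---|---|---|---|
| 60/30/10 | 22-25% | 24-40% | 0-17% | 1.10-1.18 |
| 50/30/20 | 40-43% | 30-46% | 4-12% | 1.18-1.28 |
| 34/33/33 | 58-62% | 42-57% | 5-18% | 1.30-1.47 |
| 30/30/40 | 66-69% | 45-59% | 10-22% | 1.35-1.55 |

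GU leaks have the opposite sign to GYN leaks.

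**Chance of detection.** An effect with 80% power at 1-sided 0.025 is 1.96 + 0.84 = 2.80 standard errors. If the GYN-only difference is that large, the standardised sex interaction is leak x 2.80 x sqrt[F(1 - F)].
- Smallest leak (60/30/10, F = 0.445): 0.225 x 2.80 x 0.497 = 0.31. Two-sided p < 0.05 then has probability about 6%.
- Largest leak (30/30/40, F = 0.58): 0.690 x 2.80 x 0.494 = 0.95, giving about 16%.
- With no leakage the figure is 5%. At twice the GYN difference the range is about 10% (0.091 + 0.005, both tails) to 48%.

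**The case against.** The strongest defence is that the plan already limits the harm. The analysis is exploratory, it follows up only significant effects, and its results are to be called preliminary. Randomisation protects the primary comparison whatever is done here. All of that stands.

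A reader might go further and infer that a difference between cancer types will be reported as a sex difference, or that the sex result cannot be interpreted. The documents do not support either. Both sexes are eligible, so GI and GU can each hold men and women, and the overlap is partial. Little of a GI-only difference leaks, and the interaction test would usually miss the leak.

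A reader might also take the 90-day readmission range of 23-43% by tumour site in Section 2.1 as evidence that the effect differs by diagnosis. Those are baseline risks, not treatment effects, and the procedures named there are cystectomy, esophagectomy and pancreatectomy, none of them listed as GYN surgery. They do not contradict the pooling.

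The trial will also say little about each cancer type alone. At equal thirds, the full detectable effect within one diagnosis is 2.80 / sqrt(3) = 1.62 standard errors, or about 37% power. That argues for reporting estimates with intervals, not for leaving diagnosis out.

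What the defence does not answer is the labelling. Calling a sex finding preliminary does not separate sex from cancer type, and nothing elsewhere in the plan does so.

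**Conclusion.** The point holds as a limited weakness of an exploratory analysis. Diagnosis is a stratum and is collected, yet it is neither an effect modifier nor a covariate, so the planned sex interaction mixes sex with cancer type. Over the assumed mixes, about 22-69% of a GYN-only difference, 24-59% of a GU-only difference (opposite sign) and 0-22% of a GI-only difference would pass into the sex term.

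These figures rest on a case mix that the documents do not give and on no true sex effect within a diagnosis. That GYN patients are all women is secure; that GU leans male is an assumption. Nothing here shows that the effect does differ by cancer type.

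**What to change.** In Section 13.2:
- Add an exploratory treatment-by-diagnosis interaction for both primary endpoints (step count and maximum CCI), with the effect estimate and interval for each diagnosis.
- Include diagnosis as a covariate in the Aim 1 and Aim 2 models.
- Estimate the sex interaction in a model that also contains diagnosis and treatment-by-diagnosis. It is then estimated within GI and GU, and leakage from diagnosis is zero in expectation.
- Keep all of this labelled preliminary.

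The cost is SAP wording and a few model fits on data already collected. The standard error of the sex interaction rises about 1.10-1.55 times over the assumed mixes, which reflects what the data can show about sex apart from cancer type. With one overall diagnosis test per endpoint, interaction tests on the two primary endpoints go from 4 to 6. If they were independent at 0.05, the chance of at least one false positive would rise from 1 - 0.95^4 = 19% to 1 - 0.95^6 = 26%.
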